6 TREATMENT PLAN

6.1 Administration Schedule

The treatment group will receive an oral dose of either 2.5mg or 3.125mg carvedilol twice daily for 4 weeks. The placebo group will receive a placebo pill twice daily for 4 weeks.

6.2 Treatment (Carvedilol)

6.2.1.1 How Supplied, Stored, Packaged and Labeled

Carvedilol will be supplied by Investigational Drug Services (IDS) at the University of Utah Hospital. The carvedilol capsules will be over-encapsulated for blinding. Likewise, matching placebo capsules will be produced.

The capsules will be stored at 20° to 25°C (68° to 77°F); excursions permitted to 15° to 30°C (59° to 86°F). They will be protected from light, moisture, freezing and excessive heat. They will be dispensed in a tight, light-resistant container as defined in the USP in a locked cabinet where only staff associated with the study has access to.

6.2.2 Preparation and Administration

Investigation Drug Services (IDS) will prepare the capsules with either carvedilol or placebo in a blinded fashion. Each container will have a number and will match the number the patient receives at randomization. Both the investigational staff and the patients will be blinded to the treatment that the patient is receiving. Randomization will be conducted by the Study Design and Biostatistics Center (SDBC) who will provide a randomization code to IDS. The randomization code will be stored in a central database and the file will not be opened until the study is complete or if patient safety requires it.

At randomization, the patients will each receive their own container matching the randomization number. The container will have enough capsules for the 4-week treatment period. On the day of the second hypoglycemic clamp study, the subjects will be asked to return the container including any unused capsules.

6.2.3 Accountability and Compliance

The study investigators will keep a record of the container that each patient receives. This information will be noted in the participant's clinical research file. When the patients return for the second hypoglycemic clamp study, they will bring their container and the remaining pills will be counted and noted in the clinical research file as well. The patient will also be asked to assess how often, if at all, he or she forgot to take the medication.

6.3 Duration of Therapy

The period of treatment is 4 weeks (28 days).

Subjects will be withdrawn or discontinued from the study if any of the following occurs:

- The subject withdraws consent for further participation in the clinical trial. At any time during the trial and without the need to provide a reason or rationale, a subject may choose to decline to participate further in the study. The subject will not suffer any consequences as a result.
- Subject is lost to follow-up despite efforts to contact them.
- Episodes of severe bradycardia and hypotension requiring hospitalization.
- Episodes of severe hypoglycemia develop which involve seizure development or which require hospitalization. The patient population that we are studying are Type 1 diabetic individuals with impaired awareness of hypoglycemia. Thus, these patients are at a higher risk of experiencing hypoglycemia, and it is expected that these patients will have episodes of hypoglycemia (whether treated with investigational drug or placebo). Patients are required to report all episodes of hypoglycemia. Hypoglycemic episodes can range from mild-moderate to severe. Severe hypoglycemia is defined as “hypoglycemic episodes with severe cognitive impairment requiring external assistance for recovery”. In the event the study participant experiences an episode of severe hypoglycemia, the circumstances regarding the patient's episode of hypoglycemia will be evaluated by our medical staff who have expertise in treating patients with Type 1 diabetes. Decisions will be made on a case-by-case basis as to whether it is safe for the participant to continue in the study. Obviously the severity of hypoglycemia will impact this clinical decision. Specifically, in the event the participant experiences an unexplained episode of severe hypoglycemia that involves loss of consciousness, seizures or hospitalization, the participant will be immediately removed from the study, the study drug treatment condition will be unblinded, and the IRB notified. For other cases, we will evaluate the circumstances regarding the patient's episode of hypoglycemia individually, and determine whether it is medically safe for the participant to continue in the study. If the participant is withdrawn from the study, the study drug treatment condition will be unblinded, and the IRB notified. As a part of the usual standard of medical care, any participant who experiences severe hypoglycemia will also receive education on how to avoid hypoglycemia.

Subjects may be withdrawn or discontinued from the clinical trial for the following reasons:

- The subject is non-compliant with study treatment requirements and/or protocol procedures, including the use of prohibited concomitant medications.
- The occurrence of an AE, laboratory abnormality or other medical condition or situation such that in the investigator's opinion, continued participation in the study would not be in the best interest of the subject.

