7.1 Dose Modification

In this study, participants will receive either a 2.5mg or 3.125mg of carvedilol twice daily. Patients will not have the dose increased. However, if patients experience profound side effects due to the medication such as hypotension and syncope, the PI can reduce the dose by one-half (i.e. one dose per day vs twice daily) or consider withdrawing the participant (see section 6.3). If treatment is delayed, the subject's participation in the study will be discontinued.

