collected to measure glucose, HbA1c, hematocrit and hormones (glucagon, catecholamines, insulin, cortisol, growth hormone, pancreatic polypeptide). Blood samples collected for assessment of plasma glucose (1mL) during the clamping procedure will be aliquoted into heparin coated 1ml Eppendorf tubes to prevent coagulation and processed immediately in the YSI and/or Analox Instruments glucose analyzer. In addition, the participants will be asked to fill in questionnaires to assess their perception of hypoglycemic symptoms (Edinburgh Hypoglycemia Symptom Scale) and their fear of hypoglycemia. Subsequently, the subjects will be given KCl tablets (20-40mEq) to help maintain potassium levels during the clamping procedure. Once assessment of baseline parameters has been completed, constant insulin (2mU/kg/min) and variable 20% dextrose infusions will be started at -60 minutes to establish stable glucose levels of ~90mg/dl before gradually lowering plasma glucose levels in three steps from 90-65-55-45 mg/dl by gradually reducing the glucose infusion rate. Plasma glucose levels will be monitored from a 1ml blood sample every 5min using a YSI and/or Analox glucose analyzer. A second Analox Instruments glucose analyzer and glucometer will be kept on hand as a backup. It is important that the glucose levels NOT be communicated verbally during the clamping procedure as notification of declining glucose concentrations to the participant might trigger confounding (i.e. artificially higher) awareness scores or stress hormone responses. Each glycemic step will be held for 30 minutes, allowing enough time for blood collection (~30mL at each glycemic plateau) and completion of the Edinburgh questionnaire at each glycemic plateau. At each glycemic step, plasma hormones (glucagon, catecholamines, insulin, cortisol, growth hormone, pancreatic polypeptide) will be evaluated. The frequent assessment of hypoglycemia symptom scores allows us to identify the threshold at which hypoglycemic symptoms are first noticed by the subject. We chose glycemic targets of 55 and 45mg/dl as hypoglycemic symptoms generally first appear between 55-65mg/dl in hypoglycemia aware individuals. In contrast, symptoms may not manifest in hypoglycemia unaware patients until glucose levels reach 45mg/dl. Targets of 55 and 45mg/dl allow us to safely determine whether carvedilol treatment raises the glucose threshold at which symptoms are first detected (i.e. improving hypoglycemia awareness). No more than 500mL of blood will be collected throughout the entire clamping procedure which is equivalent to the volume of a single blood donation. After the clamp, the participant's glucose levels will be recovered to normal by stopping the insulin infusion and raising the glucose infusion rate. In addition, a meal will be provided to aid recovery. This first set of clamps will establish a baseline response in the participant prior to the start of the intervention phase of the study. **Dispersal of Intervention Drug:** At the end of the clamp procedure, the subjects will be supplied with either placebo or one of two different doses of carvedilol, 2.5mg or 3.125mg, along with instructions on how to take the medication. The research staff and participant will be blinded to the treatment being received. The initial dose will be taken on the day following the clamp. In addition, the participant will also receive a hypoglycemia log book along with instructions on how to document hypoglycemia incidences and whom to contact in case of medical concerns. Once the participant's blood glucose levels are stable and he/she is ready to be discharged, we will provide them with glucose tablets and we will cover the cost of transportation home as a precautionary measure.

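### Sections 6.3 and 7.1 end study participation, not only dosing, after certain safety events and treatment delays, so those patients lose the week-4 clamp and later CGM and survey data

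*Combined protocol and SAP*

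**What the plan says.** Section 6.3 is titled as a rule about therapy, but its mandatory list opens: "Subjects will be withdrawn or discontinued from the study if any of the following occurs". Apart from withdrawn consent and loss to follow-up, the list has two clinical triggers:

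- "Episodes of severe bradycardia and hypotension requiring hospitalization".
- "Episodes of severe hypoglycemia develop which involve seizure development or which require hospitalization". The text under this bullet says continuation is decided case by case. It then makes one situation firm: after "an unexplained episode of severe hypoglycemia that involves loss of consciousness, seizures or hospitalization, the participant will be immediately removed from the study", with unblinding and IRB notification. Other severe episodes are reviewed individually.

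Section 7.1 adds that if treatment is delayed, the subject's "participation in the study will be discontinued". It gives no length of delay.

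Neighbouring rules are milder. For profound side effects, "the PI can reduce the dose by one-half" and keep the patient in. Under 6.2.3 leftover capsules are counted and "The patient will also be asked to assess how often, if at all, he or she forgot to take the medication". Withdrawal for non-compliance or for other adverse events is optional under 6.3.

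The three primary assessments in 9.11.1 (symptom scores, detection threshold and hormone responses) need the second clamp at week 4. CGM runs to the end of that clamp (9.8), and the study calendar repeats the awareness and fear surveys there. No section describes an early-termination visit, or clamp, CGM or survey collection after drug is stopped. Only adverse-event follow-up to resolution (9.12.1) could continue.

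**The concern.** Stopping study drug and leaving the study are different decisions, and the plan treats them as one. A randomised patient who meets a trigger has a baseline clamp but no post-treatment clamp, and CGM and survey data end early. The reasons for leaving (severe hypoglycemia, a hemodynamic reaction, an interrupted course) may relate to treatment or outcome, so the completers need not represent the randomised arms. With 7 per arm, each patient matters. Section 10 names no analysis set or missing-data rule for patients without a second clamp.

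The delay rule is the least justified. It names no safety event, and after a delay the clamp will often still be feasible. Section 9.12.1 lists interrupting study drug as an ordinary response to an adverse event, and the study calendar lets the second clamp slip by up to 7 days because of hypoglycemia. A delay in drug, by contrast, costs the patient's whole remaining contribution.

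**Working it through.** **The plan's own figure.** Section 10 gives 21 patients (7 per arm), power of at least 80% and a 5% significance level. It states no effect size, SD or dropout rate, so the number cannot be reproduced. Back-solving for one dose against placebo (two-sample t, two-sided 5% assumed), 7 v 7 has 80% power at a difference of 1.63 SD. That is a reference value, not a stated design effect.

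**Precision.** SE = sqrt(1/n1 + 1/n2) in SD units; half-width = t(0.975, df) × SE. Each loss is 1/7 = 14% of an arm.

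Two-group t, df = n1 + n2 − 2:

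| Completers | SE | t | 95% half-width | Power at 1.63 SD | Power at 1.0 SD |
|---|---|---|---|---|---|
| 7 v 7 | 0.535 | 2.179 | 1.165 | 80% | 41% |
| 7 v 6 | 0.556 | 2.201 | 1.225 | 76% | 38% |
| 6 v 6 | 0.577 | 2.228 | 1.286 | 72% | 35% |

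Section 10 plans ANOVA. With error pooled over three arms, df is 21 − 3 = 18, or 20 − 3 = 17 after one loss:

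- 7 v 7: 2.101 × 0.535 = 1.12 SD; power at 1.63 SD is 82%.
- 7 v 6: 2.110 × 0.556 = 1.17 SD; power at 1.63 SD is 79%.

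Neither version uses the baseline clamp.

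**Number removed and bias: an illustration for hypoglycemia removals only.** Section 2 gives 1 to 2 severe episodes a year (r). The share s that leads to removal is not given; 10% to 50% is assumed. Over 28 days the chance per patient is q = 1 − exp(−r × 28/365 × s).

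With no drug effect, expected removals are 21q and the chance of at least one is 1 − (1 − q)^21:

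- r = 1, s = 0.1: q = 0.0076; 0.16 removed; 15%.
- r = 2, s = 0.1: q = 0.0152; 0.32 removed; 28%.
- r = 1, s = 0.5: q = 0.0376; 0.79 removed; 55%.
- r = 2, s = 0.5: q = 0.0738; 1.55 removed; 80%.

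Expected bias is then zero, because removal is equally likely in each arm.

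For a 1 SD benefit, let hypoglycemia burden be N(0,1) on placebo and N(−1,1) in both carvedilol arms. Removal follows a logistic curve in burden (slope 1 or 1.5), with its intercept set so that placebo removal equals q. Total removals are 7 × placebo rate + 14 × carvedilol rate. The last two columns give the carvedilol–placebo difference among completers, whose true value is 1; the paired figures are for slopes 1 and 1.5.

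| r, s | Removed of 21 | Chance of at least one | Burden–clamp correlation 1 | Correlation 0.5 |
|---|---|---|---|---|
| 1, 0.1 | 0.09 / 0.08 | 9% / 8% | 0.995 / 0.992 | 0.998 / 0.996 |
| 2, 0.1 | 0.19 / 0.16 | 17% / 15% | 0.991 / 0.984 | 0.995 / 0.992 |
| 1, 0.5 | 0.47 / 0.40 | 38% / 33% | 0.978 / 0.964 | 0.989 / 0.982 |
| 2, 0.5 | 0.94 / 0.81 | 62% / 57% | 0.961 / 0.936 | 0.980 / 0.968 |

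The largest bias is 1 − 0.936 = 0.064, about 0.06 SD toward no effect, against an SE of 0.53 SD.

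**The case against.** The case for leaving the rules alone has real substance.

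- **Safety.** The clamp works by "gradually lowering plasma glucose levels in three steps from 90-65-55-45 mg/dl". Declining to repeat it after an unexplained seizure or loss of consciousness is reasonable. For those patients continued follow-up would save only CGM and surveys, so the hypoglycemia illustration does not measure primary data that a change would recover. This stands.
- **Wrong branch quantified.** The primary outcomes are recoverable mainly after a delay or another stop where the clamp is safe, and the documents give no rate for these. This stands. The background rate in section 2 is also not specific to impaired awareness; section 6.3 calls the trial population higher risk, so the rate may be low.
- **Estimand.** The question is about effect after 4 weeks of carvedilol. With a half-life of 7 to 10 hours (section 3), a week-4 clamp after an early stop is off drug. That is why on-drug results should be reported alongside; it does not justify discarding the assessments.

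A reader might also infer more than the text supports:

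- *That there are two separate firm hypoglycemia rules.* They come from one bullet and overlap. Whether an explained episode with seizure or hospitalization forces removal is unclear.
- *That any delay, even one missed dose, ends participation.* The sentence follows dose changes for side effects and may mean dosing held for toxicity. Missed doses are handled elsewhere.
- *That every adverse event ends participation, or that earlier data are thrown away.* Other events are discretionary, dose-halving keeps patients in, and nothing says collected data are discarded.

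**Conclusion.** The point holds as a minor design weakness. Following the rules as written removes randomised patients from assessments that are already planned, for reasons that do not always make those assessments unsafe. The firm part covers hospitalized bradycardia and hypotension, unexplained severe hypoglycemia with loss of consciousness, seizure or hospitalization, and treatment delay of undefined length.

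The size is modest. One lost patient widens the interval for one dose against placebo by about 0.05 to 0.06 SD, depending on whether three-arm or two-group error is used. It takes 3 to 4 percentage points off power at the back-solved 1.63 SD.

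A claim of serious bias is not supported. The illustration gives at most about 0.06 SD, and none if the drug has no effect. It rests on an assumed 10–50% removal share, a general background rate and an assumed link between burden and removal. It says nothing about bradycardia or delay, for which the documents give no figures.

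**What to change.** In 6.3 and 7.1, make these triggers stop study drug rather than end participation, and drop the rule that a treatment delay ends participation. State what happens after an explained severe episode. Keep the drug-stopping, unblinding and IRB rules unchanged, together with the investigator's power to end participation in the subject's best interest.

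With consent, patients who stop or delay drug continue CGM and surveys to week 4. CGM may be unblinded if the clinician judges that safer, and those data are flagged. The second clamp is done whenever judged safe, in particular after a delay; it may be omitted after an unexplained seizure or loss of consciousness.

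In section 10, analyse patients as randomised with all available data, report on-drug results alongside, and list removals by arm and reason.

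The cost is protocol and SAP wording, since the devices and visits are already planned. The downside is that off-drug data on perhaps one or two patients dilute the on-drug effect. CGM data after hypoglycemia education or unblinding are weaker evidence. Primary outcomes will probably still be missing after a seizure or loss of consciousness.

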7 TOXICITIES AND DOSE MODIFICATION

This study will utilize the CTCAE (NCI Common Terminology Criteria for Adverse Events) version 4.0 for adverse event and serious adverse event reporting.

7.1 Dose Modification

In this study, participants will receive either a 2.5mg or 3.125mg of carvedilol twice daily. Patients will not have the dose increased. However, if patients experience profound side effects due to the medication such as hypotension and syncope, the PI can reduce the dose by one-half (i.e. one dose per day vs twice daily) or consider withdrawing the participant (see section 6.3). If treatment is delayed, the subject's participation in the study will be discontinued.

7.2 Supportive Care

All supportive measures consistent with optimal subject care will be given throughout the study and all participants will be given a telephone number which they can call if they have any questions or concerns regarding the study and/or their participation in the study.

8 STUDY CALENDAR

Period	Screening	Treatment Period			
		Intervention Phase (4 weeks)			
		Baseline CGM	1 st Hypoglycemic Clamp Study	Follow-Up	2 nd Hypoglycemic Clamp Study
Visit No.	1	2	3	4	5
Week ¹	-5 to -2	-2	0	1-2	4
Assessments					
Informed consent	X				
Inclusion/Exclusion criteria	X				
Demographics	X				
Vital signs	X		X	X	X
Physical Examination	X				
Pregnancy Test	X	X	X		X
ECG	X		X		X
Hematology/Chemistry/Urinalysis ²	X				
AE Assessment		X	X	X	X
Concomitant Medications	X	X	X	X	X
CGM and Glucometer		X ³	X	X	X ³
Fear Survey			X	X	X
Hypoglycemia Awareness Survey	X			X	X
Overnight Hospital Admission			X		X
Investigational Drug Treatment			X ⁴	X	X ⁴
Primary Objective Assessment			X		X
Secondary Objective Assessment			X		X

1. All screening procedures should be completed within 4 weeks of study enrollment (Visit 1), with the exception of laboratory tests which must be completed within 2 weeks, and pregnancy test which must be completed within 48 hours of screening (Visit 1). All visits within the “Treatment Period”, except the 2nd hypoglycemic clamp study, should occur within \pm 3 days of target date. The 2nd hypoglycemia clamp may be postponed up to 7 days due to hypoglycemia prior to the clamp study.
2. Hematology labs include CGC with differential and platelets; Chemistry labs include c-peptide, HbA1c, Hemoglobin, Albumin, Alkaline Phosphatase, Aspartate Aminotransferase, Alanine Aminotransferase, Total Bilirubin, Creatinine, Glucose, Potassium, TSH, Sodium and Urea Nitrogen; Urinalysis is a dipstick urinalysis including Protein, Hemoglobin and Glucose

3. The CGM is placed after enrollment and until the completion of the second hypoglycemic clamp study. Bayer Contour Next EZ[®] glucometer will be provided to participant and they will be required to use it to monitor their blood glucose and to calibrate the blinded CGMs.
4. The investigational drug treatment is to be started after the first hypoglycemic clamp study and completed on the day prior to the second hypoglycemic clamp study.

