9.10 The Clamp Procedure

Patients will be asked to reduce the dose of long-acting insulin 24 hours prior to the clamp study if applicable. The night before the clamp study, the subjects will be admitted into the CSC and the CGMs will be checked for hypoglycemia (reading <75-80mg/dl). We are setting this cut-off a little higher than the clinical definition of hypoglycemia (<70mg/dL) to ensure central mechanisms that are normally triggered by mild hypoglycemia are not activated⁷⁵. If hypoglycemia (<75-80mg/dL) is noted within 24 hours of beginning the clamp study, then the study will be delayed for one week. Qualifying subjects will be provided with a standardized low glycemic index meal to avoid fluctuations in blood glucose levels during the overnight fast. The CSC nursing staff will introduce an intravenous (antecubital vein) insulin drip in the subject and blood glucose levels will be maintained between 90-120mg/dl during the overnight fasting period. Blood glucose concentrations will be determined from a fingerstick using a point-of-care glucometer in order to titrate the insulin drip.

First Hypoglycemic Clamp: The next day, the patient will be asked to void their bladder prior to the start of the clamping procedure. The participant will then remain in bed in a supine position for the procedure. The participant will be asked to refrain from watching television during the procedure. A second catheter will be inserted into the contralateral hand vein for blood sampling and the sampling hand placed into a heated (~55°C) box to arterialize the blood. An ECG will also be connected to the subject to monitor heart electrical activity. Heart rate, blood pressure and ECG will be monitored every 15 minutes throughout the study. Prior to the drawing of each blood sample, the deadspace volume (~5-6ml) will be withdrawn into a syringe. A new syringe will be replaced onto the luer lock and the required blood volume drawn into new syringe. Following blood collection, the collected deadspace volume will be reinfused, followed by a saline infusion through the intravenous line to clear it of residual blood. Baseline blood samples (30mL) will be

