
Follow-Up Visit: About 7-14 days after the start of the intervention phase, the subjects will be asked to come into the clinic for a follow-up visit where vital signs, AE and CGM data will be monitored or evaluated. Subjects will also be asked to complete a hypoglycemia awareness and fear survey at this time.

Second Hypoglycemic Clamp: At the end of the four-week intervention phase, the subjects will return to the CSC for the overnight stay and second hypoglycemic clamp procedure. The second hypoglycemic clamp procedure will be identical to the first described above.

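### Clamp 2 may be postponed by up to a week, but treatment duration and supply stop at 28 days, so the dosing rules cannot all be met for a postponed participant

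*Combined protocol and SAP*

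**What the plan says.** Five provisions bear on how long a participant takes study drug.

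- Start of dosing, section 9.10: "The initial dose will be taken on the day following the clamp".
- End of dosing, section 8, footnote 4: treatment is "completed on the day prior to the second hypoglycemic clamp study".
- Duration, section 6.3: "The period of treatment is 4 weeks (28 days".
- Supply, section 6.2.2: each participant gets one container at randomization. "The container will have enough capsules for the 4-week treatment period". It comes back at clamp 2: "On the day of the second hypoglycemic clamp study, the subjects will be asked to return the container including any unused capsules".
- Timing of clamp 2, section 9.10: "At the end of the four-week intervention phase, the subjects will return to the CSC for the overnight stay and second hypoglycemic clamp procedure". Section 8, footnote 1, adds: "The 2nd hypoglycemia clamp may be postponed up to 7 days due to hypoglycemia prior to the clamp study". Section 9.10 is firmer on the length of the delay: if a CGM reading below 75-80 mg/dL "is noted within 24 hours of beginning the clamp study, then the study will be delayed for one week".

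No section says whether dosing continues during a postponement, provides for overage or resupply, or limits the time between the last dose and clamp 2. Section 7.1 discontinues a participant whose treatment is delayed, but does not say whether a postponed clamp counts. Nor does the plan say what happens if the rescheduled clamp is again preceded by hypoglycemia: section 9.10 would delay it a second time, while footnote 1 allows 7 days in all.

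**The concern.** Postponement is written into the plan, in a population chosen for being prone to hypoglycemia and with a cut-off deliberately set above 70 mg/dL. It is therefore a foreseeable event, and the plan gives two answers on drug exposure when it happens. Footnote 4 ties the last dose to the clamp, so dosing would run on. Sections 6.2.2 and 6.3 tie it to 28 days, so dosing would stop.

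The primary assessment (section 9.11.1) is the clamp response after 4 weeks of carvedilol. A postponed carvedilol participant handled under 6.2.2 and 6.3 would be tested after 4 weeks on drug and about a week off it. A postponed placebo participant loses no active drug. The trigger is hypoglycemia, which carvedilol is meant to reduce, so the affected participants would not be a random subset. With 7 per arm, each one is 1/7, or 14%, of an arm.

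**Working it through.** **Inputs.** Clamp 1 is day 0. The first dose is on day 1 (9.10). Dosing is twice daily (6.1). The last dose is on the day before clamp 2 (footnote 4). Clamp 2 nominally falls at the end of four weeks, taken here as day 28 or day 29. The postponement is up to 7 days (footnote 1), or one week (9.10). Assumption: one capsule per dose and no overage.

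**Formulas.** Dosing days under footnote 4 = clamp 2 day − 1. Capsules needed = 2 × dosing days. Implied supply = 2 × 28 = 56. Full drug-free days if dosing stops after day 28 = clamp 2 day − 29, with a minimum of 0.

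**The plan's own figure.** With no delay and clamp 2 on day 29, dosing days = 29 − 1 = 28, which reproduces section 6.3. With clamp 2 on day 28, dosing days = 27 and 54 capsules are used.

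| Delay (days) | Clamp 2 on day | Capsules under footnote 4 | Against 56 | Full drug-free days if stopped at day 28 |
|---|---|---|---|---|
| 0 | 28 or 29 | 54 or 56 | 2 spare or exact | 0 |
| 1 | 29 or 30 | 56 or 58 | exact or 2 short | 0 or 1 |
| 3 | 31 or 32 | 60 or 62 | 4 or 6 short | 2 or 3 |
| 7 | 35 or 36 | 68 or 70 | 12 or 14 short | 6 or 7 |

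For the full-week delay, which section 9.10 makes the default, the shortfall is 12 to 14 capsules, or 6 to 7 days of dosing.

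**Exposure.** Section 3 gives a half-life of 7 to 10 hours. From the evening of day 28 to the morning of day 35 is 6.5 days = 156 h; to the morning of day 36 it is 7.5 days = 180 h. At most 0.5^(156/10) = 0.00002, or 0.002%, of plasma drug remains. For comparison, if the last dose is 12 to 24 h before an on-time clamp (an assumed interval), between 0.5^(24/7) = 9% and 0.5^(12/10) = 44% remains. This describes drug in plasma, not effect.

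**The case against.** The calendar's two footnotes can be read together. Footnote 1 moves the clamp, and footnote 4 attaches the end of dosing to the clamp and not to a day number. On that reading the 28 days in section 6.3 are nominal, and dosing simply continues. This is the more natural reading. A reader might infer that the plan sends postponed participants into the clamp a week off drug; the documents do not support that. It follows only if sections 6.2.2 and 6.3 are allowed to override footnote 4.

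The 56 capsules are also an inference. Enough for four weeks is a minimum, and the return of unused capsules is compatible with overage. Missed doses, or the halved dose that section 7.1 permits, would leave capsules over. The CGM check takes place at admission the evening before the clamp and the drug comes from the local drug service, so resupply would be practicable although it is not described.

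On harm, footnote 4 stops dosing the day before every clamp, and the Background (section 2) places the benefit in blockade during earlier hypoglycemia. Some effect may therefore outlast the drug. A reader might infer a definite loss of effect or of power. The documents support neither: they give no postponement rate, no persistence of effect and no effect size. No route to a false positive is evident.

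What stands is that 6.2.2 and 6.3, as written, neither supply nor permit the dosing that footnote 4 requires after a full-week delay. Two sites of authority within one protocol lead to different exposure at the primary assessment. Extending treatment does mean that some participants receive up to five weeks where section 9.11.1 speaks of four; that is a real cost, but it keeps the relation between last dose and clamp the same for everyone.

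**Conclusion.** The inconsistency holds and is minor. For a clamp postponed by a full week, footnote 4 calls for 68 to 70 capsules. The implied supply is 56, assuming one capsule per dose and no overage; shorter delays give a smaller gap. If the duration and supply sections prevail, the participant is assessed after about 6 to 7 drug-free days, contrary to footnote 4. The likely consequence is some dilution of the treatment effect, because postponed carvedilol participants would move toward the untreated state and placebo participants would not. Its size cannot be stated from the documents, since neither the number postponed nor the effect lost is given.

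**What to change.** - Footnote 4: state that twice-daily dosing continues through the day before the clamp 2 actually performed.
- Section 6.3: make the period 28 days, extended to at most 35 if clamp 2 is postponed.
- Section 6.2.2: dispense a 35-day supply, 35 × 2 = 70 capsules.
- Section 7.1: say that the rule on delayed treatment does not apply to a postponed clamp.
- Section 9.10 and footnote 1: state what happens if hypoglycemia recurs before the rescheduled clamp, given the 7-day limit.
- Case report form: record the date and time of the last dose before clamp 2.

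The cost is 14 extra capsules per participant (14 × 21 = 294 in all), a few wording changes and one added form entry. The downside is up to 7 more days of low-dose treatment for participants whose clamp is postponed.
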